	
Evaluate the addition of sarcopenia analysis into the prediction model to the response of immune checkpoint inhibitors in NSCLC

	
Specific Objectives:

	
Retrospective Study Phase

	
The primary objective of the retrospective clinical study within the I3LUNG project is to create a model that will be used in the prospective phase to compare the predictive accuracy of ML methods (created using multi-OMICs analyses) with current validated biomarkers (e.g., PD-L1 or available scores). All available jeopardized data of 2000 aNSCLC patients treated at any point with any IO-based therapy will be collected in the first 18 months of the I3LUNG project, including all the data and radiomics detailed in the "Scientific Clinical Study Design" section. This model will be used to create a first version of the Physician Decision Support System (PDSS) tool.

	
Prospective Study Phase

	
The primary objective of the prospective phases to compare the predictive accuracy of ML methods (created using multi-OMICs analyses) to current validated biomarkers (e.g., PD-L1). In this prospective part of the study, multi-OMICs data (pathology, genomics, transcriptomics, metabolomics, circulating immune profiling, microRNA signature classifier, liquid biopsy, microbiome) of 200 patients recruited by 5 cancer centers from the Consortium (INT, GHD, VHIQ,

MH and SZMC) will be collected and then integrated in the platform and used to feed the AI models learned on retrospective data, previously collected in the retrospective study phase.

Other objectives of the prospective phase in particular will include:

1. Integrate both retrospective and prospective data to improve and refine the predictive capabilities of the AI models compared to existing models;
2. Integrate radiomics signature originating from both Computed Tomography (CT) and Positron Emission Tomography–CT (PET-CT) images of the prospective cohort to refine and validate the retrospective radiomics signature;

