3. Eastern Cooperative Oncology Group (ECOG) performance status " 0-2.
4. Histologically confirmed diagnosis of stage IIIB/C-IV Non-Small-Cell Lung Cancer
5. No activating EGFR mutations or ALK/ROS1 rearrangements
6. No prior treatment for advanced disease
7. Availability of at least 1 (one) FFPE block for -omics data generation (for cohort 200 pts)
8. Clinical indication for frontline treatment with immunotherapy (alone or in combination), as first line of treatment for metastatic disease or consolidation treatment for locally advanced disease
9. Patients with untreated or unstable CNS brain metastases are allowed

Exclusion criteria for prospective phase:

1. Prior systemic treatment for NSCLC for advanced disease
2. Absence of sufficient amount of tumor tissue for -omics data generation for OMIC cohort (200 pts).
3. Unavailability or inability to comply with the requested study procedures, including compilation of QoL questionnaires and behavioral data collection (mobile app).
4. Unable to participate in the psychological study

	
Data for -omics analysis from patients considered screening-failure and, therefore, not eligible for the prospective phase of the protocol, will also be collected to feed the AI models using their real-world data generated during IO-based treatments. There is no limit for sample size in this phase and are not counted within the 200 patients who will be eligible for the multi-OMICs analysis.
																				
	
Scientific Clinical Study Design
 
I³LUNG will conduct an observational retrospective/prospective multicenter international project on advanced Non-Small-Cell Lung Cancer patients treated with IO. Its main objective is to study, train and validate the predictive accuracy of ML methods created by using real world data and multi-OMICs analyses, compared to the current standard of care biomarkers (e.g., the PD-L1).
 
The prospective study part of the project will start at month 3 and will continue up to 36 months, NSCLC patients candidates (n=200) to first-line IO-based therapy with available surgical samples (enough to perform -omics) will be enrolled.
 
In particular, will be collected the following data for Retrospective Phase (when available) and for Prospective phase:
																				

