
QoL Monitoring
 
Within the prospective part of the study, among all the prospective enroller centers (INT, GHD, MH, VHIO and SZMC) we will evaluate whether making decisions using our prediction system would lead to an improvement in patient's QoL using (i) the ad-hoc developed sensor- based monitoring system of patients' QoL and standardized PROMs and PREMs (ii) if co-shared decision-making impact QoL at least +10% compared to published prospective study data (Figure 6);
 
App Mobile
			

 
— Sistema Socio Sanitario Regione Lombardia
		OBSERVATIONAL STUDY PROTOCOL	MOD-PRO-G-03- DSC-10
---	---	---	---------------------------------

Sensor-based monitoring system of QoL This task foresees the development of a mobile application for the transparent monitoring of the patient's quality of life. It will include: an automatic cough detector system, an assessment of patient's mood state and emotional functioning, a human activities and gait recognition system and an evaluation of smartphone usage to monitor changes of social interactions and habits. Smartphone-based features collected daily will be correlated with clinical outcomes (e.g., monitoring toxicity and clinical benefit) collected at specific time points during the prospective clinical study in order to evaluate their capability to predict temporal variations of QoL, physical, social, and emotional functioning. Data collection within preliminary controlled studies are foreseen in this task to validate the app accuracy.

Using self-reported QoL measures to identify trajectories over time

Patients' lifestyle factors, daily habits, and quality of life will be collected at baseline and at baseline IO at 3, 6, 9 and 12 months and when progressive disease occurs through validated and self-reported measures. Physical activity, metabolic equivalent of task, and QoL will be assessed with the WHO Global Physical Activity Questionnaire. Moreover, patients will be administered with reliable, valid, and standardized cancer QoL measures such as EORTC QLQ-C30 , EQ-5D and lung cancer-specific QoL measures such as QLQ-LC13.

Image analysis methodology

The analytical process for the medical images will include:

- Data acquisition
- Image segmentation
- Analysis and features extraction

Data acquisition

Digital Imaging and Communications in Medicine (DICOM) medical images will be exported from the PACS system pseudonymized and uploaded to the central cloud server for Radiomics analysis.

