	
(squamous vs non-squamous), Stage (III vs IV), PD-L1 status, and treatment administered (Chemo-Immuno vs immuno-alone vs others IO combinations) will be considered.
 
AI analysis plan
 
After Ethical approval in each Cancer Center, the third part of the study will start at month 3 and will continue up to 36 months. These periods will allow sufficient time for prospective enrolment and follow-up of patients for at least for 18 months. At month 30, an intermediate version of the P-Model will be released after the collection of the first batch (~100) of patients including multi-OMICs data. At months 54, after the predictive models are build using all the data from 200 patients, the final P-Model will allow to verify if: (i) new predictive system using multi-OMICs results perform better compared to current ones (e.g., PD-L1 or other state of the art biomarkers), (ii) if the model using -omics data perform better compared to the R model, (iii) if there is any specific -omics analysis which perform better compare to other -omics, which would give more value to the model (iv) if the P-Model perform better compared to current biomarker, and compare to the R-model when applied to specific subgroups of patients (e.g., non-squamous vs squamous patients). We will consider this phase successful if the new P-models outperforms current biomarkers prediction at least for 10% in terms of correct prediction of either 2-year PFS and 2-year OS, measured with Harrel's C statistic.

	
The study is conducted in accordance with the Declaration of Helsinki Ethical Principles and Good Clinical Practices and was approved at each site by an independent local ethics committee.
 
During the clinical visit, after receiving adequate study information, the patient may sign an informed consent form, in accordance with the provisions of the local ethical regulations. The consent of the patient must be signed and personally dated by the patient and by the investigator/person designated to conduct the informed consent discussion. The signed and dated declaration of informed consent will remain at the researcher site and must be safely archived by the investigator so that the forms can be retrieved at any time for monitoring, auditing and inspection purposes. A copy of the signed and dated information and consent should be provided to the patient prior to participation.

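### A QoL gain of at least +10% over published data cannot be credited to the tool or to shared decision-making in an uncontrolled cohort, part of which enrols before any tool version can exist

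*Protocol*

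**What the plan says.** Under QoL Monitoring the protocol states that "we will evaluate whether making decisions using our prediction system would lead to an improvement" in patients' QoL. It names sensor-based monitoring and standard questionnaires as the instruments, and then adds the test of "if co-shared decision-making impact QoL at least +10% compared to published prospective study data". The same criterion appears in item 3 of the other objectives of the prospective phase. Neither place names the published source.

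The design is set under Scientific Clinical Study Design: "I³LUNG will conduct an observational retrospective/prospective multicenter international project". No section describes a concurrent control group or says whose treatment is decided with the tool.

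Four statements fix the timing:
- Retrospective Study Phase: the data for the R-Model "will be collected in the first 18 months of the I3LUNG project".
- Same section: "This model will be used to create a first version of the Physician Decision Support System (PDSS) tool". No release month is given.
- Scientific Clinical Study Design: "The prospective study part of the project will start at month 3 and will continue up to 36 months".
- AI analysis plan: an intermediate P-Model is released at month 30 after roughly 100 patients, and the final evaluation follows: "At months 54, after the predictive models are build using all the data from 200 patients".

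QoL questionnaires are scheduled at baseline, at 3, 6, 9 and 12 months, and at progression.

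**The concern.** The question is causal: does using the system, or sharing the decision, change QoL? The rule offered to answer it compares one cohort's QoL with a figure from other patients. Such a gap mixes any effect with differences in case mix, country, regimen and questionnaire timing. The cohort here is broad: ECOG 0-2, stage IIIB/C to IV, consolidation and metastatic treatment, untreated or unstable brain metastases allowed, five centres.

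The timeline adds a second problem. Patients who enter before a tool version exists cannot have had their entry treatment decision made with it, yet they count in the cohort average. The study could report a QoL benefit that the tool did not cause, or miss one that it did. This goes beyond detail that an analysis plan might supply, because the protocol itself chooses the external comparator and the threshold.

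**Working it through.** The protocol gives no sample size, power or error rate for QoL, so there is no stated figure to reproduce.

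**1. Share enrolled before each version.** Inputs from the protocol: 200 patients, entry from month 3 to month 36, milestones at months 18, 30 and 54, about 100 patients by month 30. Uniform accrual is an assumption: share before month t = (t − 3)/(36 − 3).
- Month 18: 15/33 = 45% (91 patients).
- Month 30: 27/33 = 82% (164 patients).
- Month 54: 100%.

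If instead the batch of about 100 tracks enrolment linearly to month 30:
- Month 18: 100 × 15/27 = 56 patients, or 28%.
- Month 30: 100/200 = 50%.

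If the 36 months are read as a duration (months 3 to 39), the shares are 15/36 = 42% and 27/36 = 75%, inside these ranges.

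**2. Dilution.** Effect needed among exposed patients for a cohort average of +10% = 10%/exposed share.
- 72% exposed: 10/0.72 = about 14%.
- 55% exposed: 10/0.545 = 18%.
- 50% exposed: 20%.
- 18% exposed: 10/0.182 = 55%.

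**3. Case mix alone.** Assumptions: SD 22, published mean 50-70 taken as known without error, 120-200 patients with QoL data, +10% read as relative. With no true effect and a case-mix shift of s percent, P(rule met) = 1 − Φ[(10 − s)% × mean/(22/√n)].
- s = 0: at most 0.6%.
- s = 5: 1% to 11%.
- s = 10: 50%.
- s = 15: 89% to 99%.

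In the other direction, a true +10% effect with a −10% case-mix shift nets to zero, so the rule is met at most 0.6% of the time. Chance is not the problem; comparability is.

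**4. What a within-study comparison could show.** Assumptions: SD 22, baseline correlation 0.5, a sharp switch to tool use at month 18, uniform accrual (about 90 unexposed, 110 exposed), two-sided 5%.
- Adjusted for baseline score: SE = 22 × √(1 − 0.5²) × √(1/90 + 1/110) = 2.71 points. Detectable with 80% power: 2.8 × 2.71 = 7.6 points.
- A 10% gain on an assumed mean of 60 is 6 points: power = Φ(6/2.71 − 1.96) = 60%.
- Exposure is a step in calendar time. For a step at fraction p of uniform accrual, R² with linear time is 3p(1 − p) = 3 × 0.455 × 0.545 = 0.74. Variance inflation = 1/(1 − 0.744) = 3.9.
- Also adjusted for linear time: SE = 2.71 × √3.9 = about 5.4 points. Detectable: about 15 points. Power for 6 points: Φ(6/5.35 − 1.96) = 20%.
- For means of 50 to 70 (5 to 7 points), power is about 45-73% without the time adjustment and about 15-26% with it.

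**The case against.** Several points against this stand. The first tool version has no release month, so a reader might infer that most of the cohort enrols before any tool exists. The documents do not establish that. The share before month 18 is 28-45%, and it passes half under uniform accrual only if release falls after about month 19.5. The batch of about 100 may also count patients with complete omics data rather than all those enrolled, so the range is itself uncertain.

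The +10% is attached to co-shared decision-making. The Background links shared decision-making to the patient decision aid (IPDAS) and to psychological annexes that are not shown, and none of the model dates is tied to that aid. The annexes might add a design element. However, the Background connects them to decision quality, communication, cognitive fatigue and decisional conflict, not to QoL.

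A reader might also infer that the QoL aim fails because the last scheduled 12-month visit, at month 36 + 12 = 48, precedes the final model at month 54. No section says QoL is meant to judge that model. Likewise, it might seem that tool use contaminates the accuracy validation. That is only conditional, since the protocol does not say whose treatment the tool guides.

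Finally, QoL impact is listed among other objectives. It is not a primary, secondary or exploratory endpoint, and the success rule uses Harrell's C. The scale and time point may lie in an analysis plan not shown. None of this repairs attribution: comparison with an external figure fails whatever share was exposed.

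**Conclusion.** The concern holds in this form: as written, the +10% rule cannot show that the tool or shared decision-making changed QoL. This conclusion rests on the absence of a stated concurrent control, not on any accrual assumption. The timeline makes it worse, because a substantial part of the cohort enrols before the first version can exist and all of it before the final version. The shares depend on the accrual assumptions shown. The case-mix probabilities and the power figures depend on an assumed SD of 22, an assumed mean of 50-70 and, for power, a baseline correlation of 0.5 and a sharp switch at month 18. Gradual uptake would reduce the overlap with calendar time; missing questionnaires would lower the power further.

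It would go too far to say that the study can learn nothing about QoL, or that an adjusted internal comparison would settle the matter. The primary accuracy objective is not affected by this point. The change should be made, because the objective is stated and an unsupported conclusion is easy to prevent.

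**What to change.** - In QoL Monitoring and in item 3 of the prospective objectives, drop +10% as evidence of an effect. Report the comparison with published data as descriptive, with its source named.
- Add one CRF item per patient: whether PDSS output (and which version) or IPDAS output was seen before the treatment decision. Start now, because exposure is hard to reconstruct later.
- Limit any statement on QoL to the version actually in use.
- Optionally add, as exploratory, an exposed-versus-unexposed comparison of QLQ-C30 change adjusted for baseline score and centre. State that exposure is strongly confounded with calendar time, and give results with and without a time adjustment so that the loss of precision is visible.
- If the tool guides some decisions, repeat the accuracy evaluation in unexposed patients as a sensitivity analysis only. That subset may be about 56 to 91 patients if tool use starts at month 18, against a comparison sized on 200.

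The cost is one CRF field, a short analysis on data already planned, and a weaker QoL claim.

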The retrospective part of the I³LUNG project includes the analysis of a multicentric retrospective cohort of more than 2,000 patients. This cohort will be used to perform a preliminary knowledge extraction phase and to build a retrospective predictive model for IO (R-Model), that will be used in the prospective study phase to create a first version of the Physician Decision Support System (PDSS) tool, an AI-based tool to provide an easy and ready-to-use access to predictive models, increasing care appropriateness, reducing the negative impacts of prolonged and toxic treatments on wellbeing and

	
healthcare costs. Also, CT and PET scans will be collected and a first radiomic signature will be created to feed the R-Model.
 
The prospective part of the project includes the collection and the analysis of multi-OMICs data from a multicentric prospective cohort of about 200 patients. This cohort will be used to validate the results obtained from the retrospective model through the creation of a new model (P-Model), which will be used to create the final Physician Decision Support System (PDSS) tool.

	
Overall Primary Objective

	
 • Prediction of response to immune checkpoint inhibitors in NSCLC by using clinical, biological, metabolomics, genomics, pathomics and radiomics data.
	
Secondary Objectives

	
 • Prediction of Progression-free survival (PFS) in response to immune checkpoint inhibitors in NSCLC by using clinical, biological, metabolomics, genomics, circulomics, pathomics, microbiome and radiomics data.
	
 • Prediction of Objective Response Rate (ORR) in response to immune checkpoint inhibitors in NSCLC by using clinical, biological, metabolomics, genomics, circulomics, pathomics, microbiome and radiomics data.
	
 • Prediction of Overall survival (OS) in response to immune checkpoint inhibitors in NSCLC by using clinical, biological, metabolomics, genomics, circulomics, pathomics, microbiome and radiomics data.
	
Exploratory Objectives

	
 • Added value of PET/CT into the prediction model for the Primary and Secondary Objectives.
	
 • Prediction of adverse events to immune checkpoint inhibitors in NSCLC by using clinical, biological, genomics, pathomics and radiomics data.

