Image segmentation

The pseudonymized DICOM images will be process through automatic segmentation by artificial intelligence using deep learning algorithms to recognize the lung field and automatically detect and segment the lung tumor lesions.

An independent qualified radiologist will centrally review the results and performance of the tumor segmentation algorithm.

Image features extraction

The study will extract and analyze a list of radiomics features according to the Image Biomarker Standardization Initiative (IBSI) recommendations. Features extracted from the segmented lesions will characterize different properties of the images, including:

- i) pixel intensity,
- ii) lesion shape,
- iii) lesion texture,
- iv) Fourier or wavelet-based features.

The parameters set obtained by RFE will be used to create radiomic signature following three steps:

- i) identification of cluster and possible expression patterns;
- ii) evaluation of relationship between these patterns and tumor/patient's;
- iii) generation of radiomic signature;

To remove redundancy within the radiomic information, one or two best-performing radiomic feature from each of the four-feature groups will be selected and combined into a multivariate Cox proportional hazards regression model for prediction of survival. For the training phase, feature stability will be assessed in inter-observer settings.

The radiomic signature will be developed in the first 1000 CT and PET-CT images and will be then validated in the ~1000 remaining patients. The generated and validated radiomic signature will be integrated to the R-model generated to improve its prediction and make the R-model.

Radiomic Signature

To assess the value of radiomic features to capture phenotypic differences of tumors, the features obtained by the RFE will be subjected to unsupervised clustering to reveal possible clusters of patients with similar radiomic expression patterns. For PET-CT metabolic tumor volume (MTV), total lesion glycolysis (TLG) and radiomics features such as volume and heterogeneity will be added to the analysis of PET-CT images.

The main clusters of patients will be related with other collected parameters, looking for association with tumor stage, histology etc. Finally, the generated radiomics signature will be validated and then integrated in the PDSS tool to improve prediction.

Artificial intelligence methodology

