Sample size and statistical analysis and AI analysis plan	
For the retrospective phase, we have planned to enroll patients based on a first check availability of already treated patients with IO-based therapy among centres.
 
The primary objective of the study is to compare the predictive accuracy of ML methods (created using multi-OMICs analyses) with current validated biomarkers (e.g., PD-L1 or available scores, see Table 2). Considering the number of 200 prospective cases, the study will have at least 85% power to detect a 0.1 increase in predictive accuracy as measured by the area under the ROC curve (AUC), assuming an AUC for validated biomarker alone of at least 0.6, using a one-sided z-test at a significance level of 0,050. The data are assumed to be discrete (rating scale) responses. Stratification Factors: Country (Italy or others), Gender (male vs females), ECOG PS (0-1 vs 2), Histology

---	--

 
Sistema Socio Sanitario Regione Lombardia
		OBSERVATIONAL STUDY PROTOCOL	MOD-PRO-G-03- DSC-10
---	---	---	---------------------------------

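### As written, the final P-Model is built on all 200 prospective patients and judged on the same patients, with no out-of-sample scoring stated for the AUC test or the success rule

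*Protocol*

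**What the plan says.** Under *AI analysis plan*, the month-54 step reads: "after the predictive models are build using all the data from 200 patients, the final P-Model will allow to verify if", followed by four questions. These include superiority to current biomarkers such as PD-L1, superiority to the R-Model, and "if there is any specific -omics analysis which perform better compare to other -omics". The phase counts as successful if the P-Model beats current biomarkers by 10% on Harrell's C for 2-year PFS and OS.

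Under *Sample size and statistical analysis*, the primary comparison uses the same patients: "Considering the number of 200 prospective cases, the study will have at least 85% power to detect a 0.1 increase in predictive accuracy", from a marker AUC of at least 0.6, "using a one-sided z-test at a significance level of 0,050".

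The end of *Background and Rationale* gives the cohort both roles at once: "This cohort will be used to validate the results obtained from the retrospective model through the creation of a new model (P-Model". The P-Model is then used to create the final physician decision tool.

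Three other places bear on the point:
- *Scientific Clinical Study Design* states an aim to "study, train and validate the predictive accuracy of ML methods created by using real world data and multi-OMICs analyses" but gives no method.
- *Prospective Study Phase* says the multi-omics data are "used to feed the AI models learned on retrospective data".
- The one development/validation split in the protocol concerns the retrospective radiomic signature, which "will be then validated in the ~1000 remaining patients".

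**The concern.** A model scored on the patients that trained it looks better than it is. Here that optimism would fall on one side of the comparison only. PD-L1 is not fitted, and the R-Model is trained on retrospective patients, so both are scored on patients who did not shape them.

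The retrospective cohort cannot repair this for the new layers. In the baseline data table, immunohistochemistry, circulating cells, cytokines and microRNA, ctDNA, genomics, metabolomics and microbiome are ticked for the prospective phase only. Inputs present in both phases may be learned partly from retrospective data, so the optimism sits mainly in the prospective-only layers.

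The primary test, the success rule and the ranking of -omics layers would all use this accuracy figure. The ranking has a further problem: apparent accuracy rises with the number of features in a layer, whatever their value.

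**Working it through.** **1. The protocol's power figure.** Stated inputs: N = 200, AUC 0.60 against 0.70, one-sided 5%, rating-scale data. Responder share and between-score correlation r are not stated, so they are assumed.

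For paired AUCs under the binormal (Obuchowski–McClish) approach, let a = √2·Φ⁻¹(AUC), k = non-responders/responders and m = responders. Then:
- V(a) = 0.0099·exp(−a²/2)·[(5a² + 8) + (a² + 8)/k]
- C(a,b) = exp(−(a² + b²)/4)·{[r + r/k + r²ab/2]/(4π) + [ab·r²(1 + k)/(2k)]/(16π)}
- power = Φ{(√m·0.10 − 1.645·√v0)/√v1}

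Here v0 is the variance of the difference with both AUCs at 0.60, and v1 is the variance at 0.60 against 0.70.

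With 40% responders (m = 80, k = 1.5) and r = 0.6:
- a = 0.358 and 0.742
- V = 0.1305 and 0.1237
- C = 0.0771 (both at 0.60) and 0.0717 (0.60 with 0.70)
- v0 = 2 × (0.1305 − 0.0771) = 0.107
- v1 = 0.1305 + 0.1237 − 2 × 0.0717 = 0.111
- power = Φ{(0.894 − 1.645 × 0.327)/0.333} = Φ(1.07) = 85.8%

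With 50% responders it is 87.4%. At r = 0 it is 54% and 56%. So 85% is attainable, but only with all 200 as the evaluation set and r of about 0.57 or more at 50% responders (0.59 at 40%, 0.74 at 20%).

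**2. Level of the test if the P-Model is scored on its own patients.** Simulation with n = 200:
- The marker is normal, shifted in responders by √2·Φ⁻¹(0.60) = 1.414 × 0.2533 = 0.358, which gives AUC 0.60.
- p independent noise features are added, so the attainable AUC stays at 0.60.
- The model is unpenalised and linear, fitted to all 200.
- The test is paired DeLong: z = (AUC of model − AUC of marker)/SE, rejecting above 1.645.

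| Noise features | Mean apparent AUC* | False superiority, own patients* | Same, 50% responders | False superiority, 10-fold cross-validated* | Apparent gain ≥ 0.10* |
|---|---|---|---|---|---|
| 5 | 0.63 | 11% | 15% | 0.3% | 3% |
| 10 | 0.67 | 49% | 58% | 0% | 13% |
| 20 | 0.71 | 97% | 95% | 0.7% | 62% |
| 50 | 0.81 | 100% | 100% | 0.3% | 100% |

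*40% responders, 300 runs per row; Monte Carlo error is up to about 3 points.

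The nominal rate is 5%. Cross-validated rates fall below it because noise features lower true accuracy: mean cross-validated AUC is 0.52 to 0.56.

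**3. A penalised learner.** With a cross-validated lasso scored on its own patients, false superiority was 31%/40%/48%/48% with 10/20/50/100 noise features. Penalisation reduces the problem but does not restore the 5% level.

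**4. The Harrell's C rule.** Start from a marker C of 0.60 and censor at 24 months. Reading 10% as relative (0.60 × 1.10 = 0.66), noise alone meets the rule as follows:
- Unpenalised Cox, 10/20/50 features: 9%/45%/99% of runs with 50% events, or 1%/12%/96% with 80% events.
- Cox lasso, 10/20/50/100 features: 4%/8%/17%/26% with 50% events, or 2%/2%/6%/17% with 80% events.

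Reading 10% as +0.10, unpenalised Cox gives 0%/7%/88% or 0%/0%/37%, and the lasso at most 11%.

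**5. Power under cross-validated scoring.** Let five features carry real signal, so that the attainable AUC is 0.70, and score the unpenalised linear model by 10-fold cross-validation (100/100 patients). Power was 57%/36%/23%/7% with 5/10/20/50 features in total. A larger repeat put the 5-feature figure a little under one half and the others within about three points. A penalised learner would give different figures.

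**The case against.** The strongest reply is that this is an omission of a kind usually filled by a statistical analysis plan. Fold structure and optimism correction are ordinary content for that document, which is not at hand. The figure summarising the machine-learning pipeline is also not shown. Building on all 200 is compatible with cross-validated scoring, and the phrase about all the data may only contrast month 54 with the interim model from the first batch of about 100. The aim to validate is stated.

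Much of this stands. A reader might infer that the protocol commits to scoring the P-Model on its own training patients. It does not say so, and resampling is not ruled out. What remains is that the protocol itself fixes who builds the model, who verifies it, the test and the success rule, and these are the same patients. It also describes validation as the creation of the model. An analysis plan with protected scoring would have to qualify that text.

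Screening failures, who are not counted in the 200, also contribute data to the models, but they are not named as a test set.

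It is also fair that the simulated sizes say little about the actual learner. The only feature handling described, for radiomics, reduces features to one or two per group.

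**Conclusion.** The point holds in conditional form. As written, the all-200 P-Model verifies its own superiority and no out-of-sample scoring is stated. If its accuracy is apparent accuracy, the bias favours only the P-Model. The 5% test is then exceeded in every such setting with added noise features shown above: about 15% false superiority with 5 noise features, 55% with 10, and 95% or more with 20 or more for an unpenalised linear model, against under 1% with cross-validated scoring. These sizes rest on assumed learners, feature counts and responder shares, and on added features that carry no information.

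Two stronger readings are not supported. One is that the Harrell's C success rule is equally unreliable: it is affected mainly with many unpenalised features, and little with few features or a lasso. The other is that the 85% power is wrong: it can be reproduced under plausible assumptions, though not necessarily once scoring is cross-validated. Confidence is medium, and the wording should be fixed before the model comparison is run.

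**What to change.** Amend the prospective paragraph of *Background and Rationale* and the *AI analysis plan*. State that the P-Model accuracy used for the AUC comparison, for the comparison between -omics layers and for the Harrell's C rule comes from nested cross-validated predictions in the 200, with feature selection and tuning inside the folds. Compare in the same patients with PD-L1 and with an R-Model frozen before any prospective data are used. The all-200 fit may still be the released model, but its uncorrected accuracy must not support a superiority claim.

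Two alternatives are weaker. Bootstrap optimism correction still left a false gain of at least 0.10 in 7% and 53% of runs with 50 and 100 unpenalised noise features. A hold-out of 100 patients would cut power from about 86–87% to 61–63% (r = 0.6, 40–50% responders).

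Recheck the 85% power for cross-validated scoring. If it is lower, restate it with the assumed responder share and between-score correlation.

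The cost is wording and computing, with no extra patients. Reported accuracy will be lower than the apparent figure, success will be harder to declare, and the stated power will probably fall. The cross-validated figure describes the modelling procedure rather than the single all-200 fit.
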